4.8.3. Overall survival

OS is defined as the time from C1/D1 to death from any cause, for patients who do not die before the end of the study or were lost to follow up, their OS will be censored on the last study follow-up date the patient is reported to be alive. OS (in months) is calculated as (death or censor date – date of C1/D1 + 1) / 30.4375.

Rules for selecting date of last contact are described in Table 4-2. Patients who are not known to have died prior to data cut-off will be censored at the date of last contact or clinical cut-off, whichever comes first.

Table 2 Rules for the last contact date for OS analysis

Source Data	Conditions
Date of C1/D1	No condition

Sponsor:	NeolimmuneTech, Inc.		
Protocol:	NIT-106 (ION-02)		
Document Version No.:	1.0	Document Date:	20Nov2023

Off study date	Only if patient status is reported to be alive
Start/end dates of concomitant medications	Non-missing verbatim term
Start/end dates from drug administration	Non-missing dose
Off treatment date	No condition
Tumor assessment (RECIST) date	Evaluation is marked as done.
Lab assessment date	Non-missing parameter value
Vital signs date	Non-missing parameter value
ECOG performance status date	Non-missing ECOG performance status
Start/end dates of adverse events	Non-missing verbatim term
Physical examination	At least 1 non-missing parameter value

A summary of the number and percentage of patients experiencing a death event will be provided along with median OS.

A Kaplan-Meier plot of OS will be presented by pool dose.

4.8.4. Duration of Stable Disease (DoSD)

The duration of stable disease is measured from the time measurement criteria are met for CR or PR or SD (whichever is first recorded) until the first date that recurrent or progressive disease is objectively documented or death, per RECIST v1.1 as determined by the investigator. Patients will be censored as PFS. DoSD (in months) is calculated as (event or censor date – first stable disease date + 1) / 30.4375.

DoSD analysis will be summarized based on Efficacy Population patients who had stable disease (CR or PR or SD). A summary of the number and percentage of patients experiencing an event, and the type of event (progression or death) will be provided along with median DoSD and Kaplan-Meier estimates.

A Kaplan-Meier plot of DoSD will be presented by pooled dose.

Sponsor:	NeolimmuneTech, Inc.		
Protocol:	NIT-106 (ION-02)		
Document Version No.:	1.0	Document Date:	20Nov2023

4.9. Pharmacokinetic Evaluations (NT-I7 serum concentrations)

Pharmacokinetic analyses will be conducted on participants in the PK Analysis Set.

Individual plasma concentration summary statistics will be computed using all available PK data. Individual concentration data will be listed for each participant and summarized by nominal sampling time point and visit as applicable with descriptive statistics (Mean, Std Dev, %CV, Min, Median, Max, and Geo Mean).

4.10. ADA/Immunogenicity Evaluations

Analysis of ADA data will be based on the Safety Analysis Set.

The ADA status will be defined using the baseline and postbaseline results. Anti-drug antibody negative is defined as negative results at all time points. Anti-drug antibody positive is defined as a positive result at any time point, including baseline.

The number and percentage of subjects with negative and positive ADA results will be tabulated by dose and phase.

All ADA results will be presented in a data listing, by date for unscheduled or repeated values.

NAb (neutralizing anti-drug antibody) data will be summarized and reported as number and percentage of subjects with NAb positive results per dose level by visit.

All NAb data will be listed by subject, visit and dose level.

Sponsor:	NeolimmuneTech, Inc.		
Protocol:	NIT-106 (ION-02)		
Document Version No.:	1.0	Document Date:	20Nov2023

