3. OBJECTIVES AND ENDPOINTS

This study will evaluate the safety and tolerability and assess the antitumor efficacy of NT-I7 in combination with atezolizumab (Phase 1b/2a) in patients with anti-PD-1/PD-L1 naïve or relapsed/refractory high-risk skin cancers (cSCC, MCC, melanoma). Specific objectives and corresponding endpoints for the study are outlined in Table 2.

Table 2 – Study Objectives and Endpoints

Objectives	Corresponding Endpoints
Primary Objective	

To evaluate the safety and tolerability of NT-I7 in combination with atezolizumab (Phase 1b), including estimation of the Maximum Tolerated Dose (MTD) and/or the Recommended Phase 2 Dose (RP2D)
 
Phase 2a: To evaluate the Objective Response Rate (ORR) according to RECIST v1.1 and iRECIST, as determined by the investigator
	
 - Incidence, nature, and severity of adverse events graded according to NCI CTCAE v5.0 - Incidence and nature of DLTs - Potential correlation with PK, pharmacodynamic, safety, and efficacy parameters - Objective Response Rate (ORR), defined as the percentage of patients who have at least one confirmed partial response (PR) or complete response (CR) according to RECIST v1.1 and iRECIST, as determined by the investigator
Secondary Objectives	

To evaluate immunogenicity of NT-I7 in combination with atezolizumab
 
To make a preliminary assessment of the anti-tumor activity of NT-I7 in combination with atezolizumab
	
 - Incidence of anti-drug antibody (ADA) to NT-I7 during the study relative to the prevalence of ADA at baseline - Disease Control Rate (DCR), defined as proportion of patients with a best overall response of CR, PR or stable disease (SD). - Duration of objective response (DOR), defined as the time from the first occurrence of a documented objective response to the time of the first documented disease progression or death from any cause, whichever occurs first, per RECIST v1.1 and iRECIST as determined by the investigator - Progression Free Survival (PFS), defined as the time from the first study treatment (Cycle 1, Day 1) to the first occurrence of progression or death from any cause, whichever occurs first, per RECIST v1.1 and iRECIST as determined by the investigator - Overall survival (OS), defined as the time from first study treatment (Cycle 1, Day 1) to death from any cause
Exploratory Objectives	

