12.3 Special Studies

12.3.1 *Immunogenicity Testing (NT-I7)*

The formation of ADA and neutralizing anti-drug antibodies (NADA) to NT-I7 will be evaluated at: Pre-treatment with NT-I7 (Cycle 1, Day 1) and on Day 1 of each subsequent cycle. Immunogenicity testing will be repeated at the end of treatment visit.

Patients who have positive ADA will be followed every 3 months for PD biomarkers including ALC, and serum IL-7 level until ADA level becomes undetectable.

NeoImmuneTech has transferred and revalidated the assay method to BioAgilytix for performing the assays and the determination of the main ADA/NADA parameters.

12.3.1.1 *Collection of Specimen(s)*

Whole blood will be collected in SSTs at each of the time points specified in the [Study Calendar](#). Please refer to the ION-02 Laboratory Manual.

12.3.1.2 *Handling of Specimen(s)*

Blood samples will be handled as per the draw tube manufacturer's recommendations, processed at the local labs into serum aliquots, and aliquots stored frozen at -80°C until shipped to the CIML.

12.3.1.3 *Shipping of Specimen(s)*

Frozen samples will be batch-shipped quarterly, or immediately upon collection of EOT visit from the clinical sites overnight on dry ice to the CIML. Sites will utilize BSI Engage to communicate with the CIML. The CIML will coordinate the shipment of samples to BioAgilytix.

12.3.1.4 *Site(s) Performing Correlative Study*

Assays will be performed by BioAgilytix, Durham, NC.

12.3.2 *NT-I7 Pharmacokinetics*

PK samples will be collected on all patients (dose escalation and dose expansion phase). Serial samples will be assessed following the PK timepoints in the tables below.

Note: The precise NT-I7 administration time and the precise PK draw time should be recorded accurately and prospectively to fully interpret these values. Blood draws are timed after NT-I7 administration is complete, not completion of atezolizumab infusion.

12.3.2.1 *Collection of Specimen(s)*

Blood draws will be performed by venipuncture on study subjects before, during, and at end of treatment.

Table 5 – Pharmacokinetic Timepoints

Dose Escalation (Phase 1b) – all patients

Pharmacokinetics										
Treatment Cycle/Visit	Cycle 1					Cycle 3		Cycle 5		End of Tx
Scheduling Window	Day 1			Day 2*	Day 8 ± 2	Day 1		Day 1		30 days ± 5
Hours	0	2 (±5mins)	6 (±15mins)	24 (±30mins)		0	2 (±5mins)	0	2 (±5mins)	
PK	X ^a	X ^b	X ^b	X	X	X ^a	X ^b	X ^a	X ^b	X

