2.5.2. Pharmacokinetics and Pharmacodynamics Variables

To evaluate the pharmacokinetics of NT-17 administered in combination with atezolizumab:

- Serum concentration of NT-17 will be used to estimate the following parameters: Area under the concentration time-curve (AUC), Maximum serum concentration (C_{max}), Minimum serum concentration (C_{min}), Clearance (CL) to be completed by Third Party Vendor.

To evaluate the immunogenicity of NT-17, the following endpoint will be analyzed:

- Incidence of anti-drug antibody (ADA) to NT-17 during the study relative to prevalence of ADA at baseline, defined as ADA titer relative to baseline to Day 1 of each cycle.

To evaluate the effect of the investigational treatment combination on the tumor microenvironment, based upon baseline and post-baseline tumor biopsy, the following endpoints will be assessed, but are outside of the scope of this plan:

- Number, distribution, and phenotype of tumor-infiltrating cells
- Expression of Interferon γ (IFN γ) and associated inflammatory gene expression in the tumor microenvironment

Sponsor:	NeolimmuneTech, Inc.		
Protocol:	NIT-106 (ION-02)		
Document Version No.:	1.0	Document Date:	20Nov2023

- Changes in tumor microenvironment that correlate with response or provide information on potential actionable causes for lack of clinical benefit

Potential correlation with PK, pharmacodynamics (PD), safety, and efficacy parameters can be explored but are outside of the scope of this plan.

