5. CHANGES TO PLANNED ANALYSES

Due to the premature closure of the study the following changes are made in comparison to the protocol:

- AEs leading to withdrawal and DLTs will not be listed separately.
- Laboratory values will only be listed.
- irRC (iRECIST) will not be summarized.
- Efficacy summaries will be performed on Efficacy Population only.
- All phases will be summarized within the same table.
- Duration of Stable Disease will replace Duration of Response analysis, due to limited patient responses.

Sponsor:	NeolimmuneTech, Inc.		
Protocol:	NIT-106 (ION-02)		
Document Version No.:	1.0	Document Date:	20Nov2023

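### The only ADA table in the SAP counts patients positive only before dosing, so it does not report the baseline-relative endpoint, and the change is not declared

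*SAP*

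**What the plan says.** Protocol section 3 (Table 2) sets the secondary endpoint as "Incidence of anti-drug antibody (ADA) to NT-I7 during the study relative to the prevalence of ADA at baseline". SAP section 2.5.2 repeats it and makes it operational: "defined as ADA titer relative to baseline to Day 1 of each cycle". Both wordings need a comparison with the pre-dose sample.

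The analysis in SAP section 4.10 uses one status per patient over the whole study. On one side, "Anti-drug antibody negative is defined as negative results at all time points"; on the other, "Anti-drug antibody positive is defined as a positive result at any time point, including baseline". The planned summary is: "The number and percentage of subjects with negative and positive ADA results will be tabulated by dose and phase". Beyond that, ADA results are only listed. The one by-visit summary in 4.10 is for neutralizing antibodies. The analysis set is all dosed patients.

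The samples for a baseline comparison are scheduled. Protocol section 12.3.1 has testing at "Pre-treatment with NT-I7 (Cycle 1, Day 1) and on Day 1 of each subsequent cycle", and again at the end-of-treatment visit.

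The end of SAP section 1 undertakes to set out where the planned analyses differ from the protocol. Section 5 opens "Due to the premature closure of the study the following changes are made in comparison to the protocol" and lists six changes. None concerns ADA.

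**The concern.** A patient who is ADA-positive before any NT-I7 and never changes is counted the same way as a patient who develops antibodies on NT-I7. The resulting percentage is neither baseline prevalence nor treatment-emergent incidence, and a reader cannot recover either from it. A titer rise in a patient already positive at baseline is invisible, although SAP 2.5.2 names titer relative to baseline.

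The SAP therefore disagrees with itself (2.5.2 against 4.10) as well as with the protocol. It applies the right principle to adverse events: section 4.11.1 counts events that start after dosing or worsen from baseline. ADA has no equivalent rule.

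What is at stake is the reported immunogenicity of NT-I7. Phase 1b cohorts have 3 or 6 patients, so a single misattributed patient changes a dose level's rate noticeably.

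**Working it through.** **No figure to reproduce.** Neither document gives an ADA prevalence, incidence or sample-size basis. The text is compared first, and the size is then shown under assumed rates.

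**Text comparison**

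| Needed for the endpoint (protocol Table 2, SAP 2.5.2) | Planned in SAP 4.10 |
|---|---|
| Baseline prevalence | No row |
| Newly positive on study | No category; merged with baseline positives |
| Titer change from baseline | No summary |
| Declared if dropped | Not among the six changes in section 5 |

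**Assumptions.** b = share positive at baseline; t = incidence among baseline-negative patients; k = share of baseline positives with a titer boost. Every patient has a baseline and a post-baseline sample.

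- Rate in the SAP 4.10 table: b + (1 − b)t
- Treatment-emergent rate over all patients: (1 − b)t + bk
- Excess over the treatment-emergent rate: b(1 − k), which runs from 0 (b = 0 or k = 1) to b (k = 0)
- Excess over incidence among baseline negatives: b + (1 − b)t − t = b(1 − t)

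| b | t | SAP 4.10 rate | Treatment-emergent, k = 0 to 1 | Excess over t |
|---|---|---|---|---|
| 0% | 10% | 10% | 10% | 0 points |
| 5% | 10% | 0.05 + 0.95 × 0.10 = 14.5% | 9.5–14.5% | 4.5 points |
| 10% | 0% | 10% | 0–10% | 10 points |
| 10% | 30% | 0.10 + 0.90 × 0.30 = 37% | 27–37% | 7 points |
| 20% | 10% | 0.20 + 0.80 × 0.10 = 28% | 8–28% | 18 points |

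**One table, three different truths.** Take 24 patients, 6 of them ever positive. The table shows 6/24 = 25% in each case below.

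- None positive at baseline: incidence 6/24 = 25%
- Three positive at baseline: incidence 3/21 = 14.3%
- All six positive at baseline: incidence 0/18 = 0%

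**Small cohorts.** One patient positive only at baseline gives 1/3 = 33.3% or 1/6 = 16.7% in a Phase 1b cohort, and 1/60 = 1.7 points in the planned Phase 2a. The trial closed early, so the real Phase 2a denominator may be smaller than 60. The chance of at least one baseline positive among n patients is 1 − (1 − b)^n:

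| b | n = 3 | n = 6 |
|---|---|---|
| 2% | 5.9% | 11.4% |
| 5% | 14.3% | 26.5% |
| 10% | 27.1% | 46.9% |
| 20% | 48.8% | 73.8% |

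**Patients with no post-baseline sample.** Read literally, a patient whose only sample is a negative pre-dose one satisfies "Anti-drug antibody negative is defined as negative results at all time points". Such a patient enters the table as ADA-negative and dilutes incidence, so the table can also err downwards.

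**The case against.** The best defence is that nothing is lost and nothing is hidden. The listing holds every ADA result, and in cohorts of 3 or 6 a reader can work out baseline and emergent status by hand. The positive category states openly that it includes baseline. Protocol 15.5.1 promises only descriptive counts and percentages for immunogenicity, which 4.10 supplies. The endpoint is secondary, no p-values are planned, and protocol 11.2.3 says the numbers are too small for firm conclusions. Protocol section 15 also allows changes to non-confirmatory analyses to be reported in the clinical study report. The table shells that the SAP mentions are not in the text available, so a baseline split there cannot be excluded.

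Much of this stands as a limit on importance. It does not remove the mismatch. A listing is not a summary of the endpoint, and hand derivation would proceed with no agreed denominator or titer threshold. The by-visit table covers neutralizing antibodies, not binding ADA. Unseen shells do not override the SAP's written rule. The SAP itself undertakes to set out its differences from the protocol, and this one is missing.

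Two further points have partial force. SAP 4.2.1 gives categorical tables a missing-data category and 4.2.8 rules out imputation in general, but neither says whether a patient with only a negative baseline sample is negative or missing. Separate induced and boosted categories are one convention among several, and in a cohort of 3 the boosted denominator would often be 0 or 1. A baseline-by-post-baseline cross-tabulation with a titer summary would also serve.

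**Conclusion.** The point holds. As written, SAP 4.10 does not deliver the endpoint in protocol Table 2 and SAP 2.5.2, and section 5 does not say so. The textual finding needs no assumption. The numerical effect does: it depends on baseline prevalence and the boosted share, which the documents do not give. Against treatment-emergent ADA the overstatement lies between zero and the baseline prevalence; it is zero if no patient is positive at baseline or all baseline positives are boosted. This is a reporting fault in a secondary, descriptive endpoint. It affects no sample size, error rate, dose rule or primary result, but it should be corrected before the immunogenicity results are summarised.

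**What to change.** In SAP 4.10, tabulate by dose and phase:

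1. Baseline ADA prevalence, among patients with a baseline sample.
2. Treatment-induced ADA: negative at baseline and positive at any later sample, among baseline-negative patients with a post-baseline sample.
3. Treatment-boosted ADA: positive at baseline with a titer rise above a threshold set beforehand, among baseline-positive patients with a post-baseline sample.

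Report treatment-emergent ADA as the patients in (2) plus (3), over those with a baseline and at least one post-baseline sample. State how many patients lack a post-baseline sample. The any-time rate can stay as an extra row, and the by-visit neutralizing-antibody table needs no change. If the single table is kept instead, declare it in SAP section 5 as a departure from the protocol endpoint.

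The cost is SAP wording, three derived categories, additional denominators and a titer-rise threshold. Neither document gives that threshold, so it must be fixed before the data are summarised. No new samples are needed. The drawback is that patients without a post-baseline sample leave the incidence denominator, which is why their number has to be shown.

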4.11. Safety Analyses

Safety analyses will be conducted using the Safety Population.

4.11.1. Adverse Events

Adverse events will be coded using the Medical Dictionary for Regulatory Activities (MedDRA) and displayed in tables and listings using System Organ Class (SOC) and Preferred Term (PT). AE severity will be graded according to the CTCAE v5.0.

Analyses of adverse events will be performed for those events that are considered treatment emergent, where a treatment emergent adverse event (TEAE) is defined as any adverse event with an onset date on or after the administration of study treatment through the end of the study (defined as 30 days after the last dose of study treatment) or any event that was present at baseline but worsened in intensity or was subsequently considered drug-related by the investigator through the end of the study.

The number and percentage of patients with any TEAE will be reported, TEAEs with CTCAE Grade 3 or Higher, TEAEs assessed by the Investigator as related to treatment (definite, probable, or possible relationship), Treatment-related TEAE with Grade 3 or Higher, TEAEs leading to NT-17/atezo Interrupted (also Dose Reduced and Withdrawn), Adverse Events of Special Interest (AESI; as designated by the CRF), Serious TEAEs, Serious Treatment-related TEAE, and TEAEs leading to Death; summarized by SOC and PT. In these tabulations, each patient will contribute only once in each category regardless of the number of events.

No formal hypothesis-testing analysis of adverse events incidence rates will be performed.

All adverse events occurring on study will be listed in by-patient listings.

By-patient listings also will be provided for the following: patient deaths and serious adverse events.

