6.6 Duration of Follow-Up

The active study will end when the last patient completes the 90-day Safety Follow-up visit, approximately 27 months after enrollment.

End of treatment (EOT) visit should be performed 30 (\pm 5) days after the last administration of either agent or immediately before initiation of any other cancer therapy. At the EOT visit, tumor assessments are only required if not performed within the past 9 weeks (for patients who are on the study for \leq 18 weeks) or 12 weeks (for patients who are on the study for $>$ 18 weeks).

Safety Follow-up visit should be performed 60 (\pm 7) days and 90 (\pm 7) days after the last administration of either agent.

Patients who permanently discontinue study treatment for reasons other than objective RECIST disease progression should continue to have RECIST scans performed every 12 weeks (\pm 1 week), at the investigative site or locally, up to 12 months after discontinuation of study treatment. Standard of care disease assessments will be collected until the start of a new anticancer treatment, disease progression, pregnancy, death, withdrawal of consent or end of study, whichever occurs first.

After disease progression or start of new anticancer treatment, patient will be followed for survival every 12 weeks (\pm 1 week) until death, loss to follow-up, withdrawal of consent or the end of the study, whichever occurs first. Survival follow-up can be done either by in-person visit or by telephone assessment.

Patients removed from study for unacceptable AE(s) will be followed until resolution or stabilization of the AE; in addition, the patients will be followed for disease status and overall survival, as described above.

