8. ADVERSE EVENTS: ASSESSING AND REPORTING REQUIREMENTS

An AE is defined as any untoward medical occurrence in a patient or clinical investigation subject administered a pharmaceutical product, and which does not necessarily have to have a causal relationship with the treatment. An AE can therefore be any unfavorable and unintended sign (including an abnormal laboratory finding, for example), symptom, or disease temporally associated with the use of a medicinal product or protocol-specified procedure, whether or not considered related to the medicinal product or protocol-specified procedure. Any worsening (i.e., any clinically significant adverse change in frequency and/or intensity) of a preexisting condition that is temporally associated with the use of the study product is also an AE.

All AEs that occur on study, within 30 days of the last administration of the study treatment, must be reported. The reporting timeframe for AEs meeting the criteria of SAE is described in Section 8.3.1.

AEs are reported in a routine manner during the trial using the EDC system. Additionally, certain AEs must be reported in an expedited manner for timelier monitoring of patient safety and care. The following list of AEs (Section 8.1) and the characteristics of an observed AE (Section 8.2 and 8.3) will determine whether the event requires expedited reporting to the ION Coordinating Center.

Electronic monitoring of AEs will be done in the following ways: through the EDC system by the ION Coordinating Center, through email reporting by each clinical site to the ION Coordinating Center and by onsite monitoring of the clinical sites. Per GCP, all sites must enter data in a timely manner. AEs meeting the criteria of SAE will be triggered in the EDC system and email notification will be sent to the ION Coordinating Center for immediate review and distribution, as required by regulatory authorities.

The investigator or qualified designee will assess each patient to evaluate for potential new or worsening AEs at the time points specified in the [Study Calendar](#) and more frequently if clinically indicated.

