2. STUDY DESIGN

2.1. Synopsis of Study Design

This is a Phase 1b/2a, open-label, multicenter study to evaluate the safety, tolerability and anti-tumor effect of NT-17 (recombinant human interleukin 7 [rhIL-7]-hybrid Fc [hyFc]) in combination with atezolizumab (MPDL3280A) in patients with anti-PD-1/PD-L1 naïve or relapsed/refractory high-risk skin cancers including cSCC, MCC and melanoma.

This study has been designed to allow for an investigation of MTD or RP2D of NT-17 in combination with atezolizumab. There are two phases to this study:

[figure not shown]
- Phase 1b, a NT-17 dose escalation phase to determine the MTD or RP2D
- Phase 2a, a non-randomized parallel dose expansion phase to confirm the MTD or RP2D in both arms

Arm I: Anti-PD-1/PD-L1 (checkpoint inhibitors [CPI]) naïve patients with cSCC and MCC
Arm II: Anti-PD-1/PD-L1 relapsed/refractory patients with MCC, cSCC and melanoma

Number of Patients

Approximately 84 patients will be enrolled; up to 24 patients will be enrolled in the Phase 1b (3 + 3 dose escalation design will be used), and approximately 60 patients will be enrolled in the Phase 2a (24 patients in Arm I, i.e., 12 patients for each indication, and 36 patients in Arm II, i.e., 12 patients for each indication).

Sponsor:	NeolimmuneTech, Inc.		
Protocol:	NIT-106 (ION-02)		
Document Version No.:	1.0	Document Date:	20Nov2023

Figure 1 Phase 1b\2a Schema

Each patient will participate in the trial ("enrolled") from the time the Informed Consent Form (ICF) is signed through final protocol-specified contact. The active study will end when the last patient completes the 90-day safety follow up visit, approximately 27 months after enrollment. Trial is expected to be completed approximately 36 months after the last patient is enrolled.

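### All AE incidence tables stop 30 days after the last dose, although AEs are to be evaluated at 60 and 90 days: reconcile the windows and add a day-90 summary

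*SAP*

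**What the plan says.** Table 2 in protocol Section 3 gives the first endpoint under the primary objective as "Incidence, nature, and severity of adverse events graded according to NCI CTCAE v5.0". That wording contains no time window.

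On analysis, SAP 4.11.1 states: "Analyses of adverse events will be performed for those events that are considered treatment emergent". It sets the upper limit as "through the end of the study (defined as 30 days after the last dose of study treatment". The second limb of the definition (an event present at baseline that worsens or is later judged drug-related) ends at the same point. The tables for Grade 3 or higher, related, serious, special-interest and fatal events all sit under this restriction.

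The same section plans two kinds of listing with no 30-day limit stated: "All adverse events occurring on study will be listed in by-patient listings", and "By-patient listings also will be provided for the following: patient deaths and serious adverse events".

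On the end of the study, SAP 2.1 says: "The active study will end when the last patient completes the 90-day safety follow up visit". SAP 4.4 also tabulates completion of the 60- and 90-day visits.

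Protocol Section 8 sets the reporting rule: "All AEs that occur on study, within 30 days of the last administration of the study treatment, must be reported". Sections 11.1.1 and 15.6.1 make patients evaluable for toxicity over the same 30 days. Against this, Section 6.6 schedules safety visits at 60 and 90 days after the last administration of either agent, each with a 7-day window. Section 7 has adverse events of all grades evaluated at every study visit throughout participation. The Section 10 calendar carries the adverse-event and immune-related-event rows into the post-treatment columns. Footnote 1 to the Section 8.3.1 table requires reports of serious events after day 30 that are possibly, probably or definitely related.

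**The concern.** The plan arranges to observe patients for late toxicity and then gives those observations no place in the incidence tables. A related Grade 3 immune event with onset on day 45 would be evaluated at the 60-day visit and, if serious, reported within 24 hours. It would still add nothing to any numerator in the safety tables.

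Safety and tolerability is the Phase 1b primary objective, and both agents act on the immune system. Protocol Section 7 itself describes autoimmune inflammatory conditions as a general risk of treatments intended to enhance T-cell responses. A reader who takes the tables as the answer to the primary question would see incidence only to day 30, under a label suggesting that the study ended there.

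**Working it through.** The plan states no figure for this point, so there is none to reproduce. The check traces example events through the documents, followed by day arithmetic and a scale calculation under assumed rates.

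**Where events go.** Days are counted from the last dose of study treatment.

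| Event | Incidence tables (SAP 4.11.1) | Elsewhere |
|---|---|---|
| Related AE, onset day 20, death day 50 | Counted, including as leading to death, because the window is set by onset | Death listing; OS if in the Efficacy Population |
| Related Grade 3 serious AE, onset day 45 | Not counted | Reported under Section 8.3.1, footnote 1; SAE listing |
| Fatal AE, onset day 45 | Not counted | Death listing; OS if in the Efficacy Population |
| Non-serious immune-related AE, onset day 45 | Not counted | Evaluated at the 60-day visit; its place in the AE listing depends on which end of study applies |
| DLT | Not affected | 21-day window (protocol 6.2, SAP 4.2.13) |

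The OS entries carry a condition. SAP 3.1.2 and 4.8 analyse OS in the Efficacy Population, which requires at least one cycle and one evaluable post-baseline tumor assessment. A patient who dies before any such scan is in neither OS nor, if the fatal event began after day 30, the fatal-event table.

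**Days covered.**
- Scheduled post-treatment safety period: 90 days (protocol 6.6).
- Tabulated period: 30 days (SAP 4.11.1).
- Not tabulated: 90 − 30 = 60 days; 60/90 = 67%.
- With the 7-day allowance on the last visit: 97 − 30 = 67 days; 67/97 = 69%.
- The end-of-treatment visit falls at 30 ± 5 days, so an event with onset on days 31 to 35 can be found at that visit and still fall outside the tables.

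**Scale, for illustration.** The documents give no rate of onset after day 30. Let p be the assumed proportion of patients with a qualifying event starting on days 31 to 90. The expected number left out is N × p, and the chance of at least one is 1 − (1 − p)^N. N is about 84 overall and up to about 24 in Phase 1b.

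| Assumed p | N = 84: expected | N = 84: chance of ≥1 | N = 24: expected | N = 24: chance of ≥1 |
|---|---|---|---|---|
| 1% | 0.8 | 57% | 0.2 | 21% |
| 2% | 1.7 | 82% | 0.5 | 38% |
| 5% | 4.2 | 99% | 1.2 | 71% |
| 10% | 8.4 | over 99% | 2.4 | 92% |

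SAP Section 5 reports premature closure, so the actual N may be lower and these figures with it.

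**The case against.** The best defence is that 30 days is the protocol's own window. Sections 8, 11.1.1 and 15.6.1 all use it, and the SAP follows them. On this view, observing patients for longer than the tabulated period is a design choice, and only the SAP's label for day 30 is wrong. The first part stands: a reader might infer that the SAP departs from the protocol, and it does not. The conflict lies inside the protocol and the SAP inherits it. Agreement with one side of that conflict does not settle it.

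The second defence is that the listings and OS capture late serious events and deaths. This also stands, as far as it goes. It would be wrong to infer that late deaths disappear from reporting. But a listing gives no incidence, and OS covers only the Efficacy Population.

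Three stronger readings are tempting and unsupported:

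- *Non-serious late events need never be reported.* Sections 8.3.2 and 8.3.3 require special-interest events to be reported regardless of seriousness, with no 30-day limit in the visible text. The lists of those events are blacked out, and Section 8.4 on routine reporting does not appear in the public text. The most that can be said is that collection after day 30 may be incomplete.
- *The window is shorter than one NT-I7 dosing interval (30 of 42 days).* The window runs from the last dose of study treatment, and atezolizumab is given every 21 days. A patient with one NT-I7 dose who receives atezolizumab on Cycle 2 Day 1 is covered for 21 + 30 = 51 days. The shortfall arises only if both agents stop after Cycle 1 Day 1 on the six-week schedule, which began at Dose Level 4.
- *Patients who stop early are undercounted most.* Everyone has the same 30 days after the last dose. Toxicity arising on treatment and leading to discontinuation is already in the tables, and Section 6.6 follows patients removed for unacceptable toxicity until resolution or stabilization. Nothing in the documents shows a larger loss in this group.

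**Conclusion.** The concern holds in a limited form. Followed as written, the plan leaves related events with new onset on days 31 to 90 out of every incidence table for the primary safety endpoint, and the SAP gives two different ends of the study. The untabulated period is 60 of 90 scheduled post-treatment days. That 67% is a share of scheduled days after treatment, not of events or of total safety observation, since treatment may run for up to 2 years. The number of events affected cannot be derived from the documents.

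The conclusion rests on reading the window as one of onset, as SAP 4.11.1 words it, and on the calendar's post-treatment marks applying to the safety visits. The calendar's columns are imperfectly aligned in the public copy, but Section 7 supports that reading independently. The change is worth making because the visits and the late serious-event reports are already planned. It does not affect the DLT assessment.

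**What to change.** 1. **SAP 4.11.1 and 2.1:** define the end of the study once. In the treatment-emergent definition, state 30 days after the last dose simply as the window, without calling it the end of the study. Say whether the by-patient AE listing covers days 31 to 90.
2. **Protocol 8, 11.1.1 and 15.6.1:** reconcile the 30-day reporting and evaluability rules with the evaluations required at 60 and 90 days, so that events found at those visits have a stated collection rule.
3. **SAP 4.11.1:** keep the 30-day tables unchanged. Beside them, add a summary to day 90, or to the start of new anticancer therapy if earlier, of serious events, treatment-related events, special-interest or immune-related events, and events leading to death.
4. **Footnote to that summary:** non-serious events after day 30 may be incompletely collected, given the 30-day reporting rule and premature closure.

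The cost is a short protocol clarification, matching CRF guidance and one added set of tables; no visit is added. Some late events will be hard to attribute, which the cut at new anticancer therapy limits. Because the study closed early, amending the protocol cannot recover non-serious events that were never recorded. The summary of late related serious events remains feasible, since their reporting was already required.
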